#### 4.4 END OF STUDY DEFINITION

A participant is considered to have completed the study if he or she has completed the online survey questionnaire that is emailed on Day 90, as shown in the Schedule of Activities (SoA), Section 1.3. The end of the study is defined as 96 days after the last participant is enrolled or when that participant completes the Day 90 survey questionnaire, whichever is sooner.

### 5 STUDY POPULATION

#### 5.1 INCLUSION CRITERIA

In order to be eligible to participate in this study, an individual must meet all of the following criteria:

1. Able to provide consent to participate in research
2. Stated willingness to comply with all study procedures and availability for the duration of the study
3. Male or female, age 13 or older
4. An ongoing low back-pain problem that has persisted at least 3 months and has resulted in pain on at least half the days in the past 6 months.
5. Ability to comprehend spoken and written English
6. Owns a compatible android or iOS smartphone, or personal laptop or desktop computer (excluding tablets) to complete surveys and has access to email.

## 5.2 EXCLUSION CRITERIA

An individual who meets any of the following criteria will be excluded from participation in this study:

1. Presents with a condition that interferes with VR usage, including history of seizure, facial injury precluding safe placement of headset, significant visual or hearing impairment that impacts ability to see the VR images or follow audio instructions
2. Are being recommended for long-term hospitalization that would require more than three-week stay in the hospital
3. Received surgical procedure within the previous 8 weeks
4. Surgery is planned within the next 3 months
5. Is currently using a spinal cord stimulator
6. Has LBP attributable to a recognizable, specific pathology, including spinal infection, cancer, fracture, or inflammatory spondylopathies, consistent with the NIH Task force on Research Standards for cLBP
7. Previously participated in a VR clinical trial

Women who are currently pregnant or planning to become pregnant will not be excluded from the study

## 5.3 LIFESTYLE CONSIDERATIONS

NA

## 5.4 SCREEN FAILURES

All aspects of this study are conducted remotely, including the participants' use of a VR therapy headset and FitBit watch at home and collection of all PROs via survey questionnaires administered electronically. In addition, the VR headset has independent value. To ascertain their willingness and ability to respond to survey questionnaires delivered by email, potential participants are required to respond to a daily electronic, one-item, "Pain Diary" question and complete the baseline survey questionnaires over the course of a "Screening Week," following informed consent but prior to randomization. A screen failure is defined as a participant who completes fewer than 86 items on the large survey on the 4th day of the screener week as well less than 5 daily "pain diary questions. Participants are required to complete this by the 7th day of the screener week or within 48hrs of being sent a reminder email to complete the survey. Participants will be sent a manual reminder email if they complete less than 80% of the large survey on the 4th day of screener week as that patient population would not get reminder otherwise from the REDCap system. Age, race, and Hispanic ethnicity are some of the information that will be collected for all participants even if they fail to complete the Screening Week questionnaires. Individuals who inform investigators during the Screening Week that they are no longer able or willing to participate in the study for any reason or who are discovered to meet any of the exclusion criteria will be recorded. Individuals who satisfactorily complete the Pain Diary and baseline survey questionnaires will be enrolled and randomized.

## 5.5 STRATEGIES FOR RECRUITMENT AND RETENTION

The target sample size is 360. We expect a representative sample of the chronic low back pain patient population seen at Cedars-Sinai. Approximately 58% are female and 42% male. For the first half of the

study, we anticipated patients who identify as white to make up about 76% of the study population, with 12% black or African American, 5% Asian, and 6% who identify as multiracial. Approximately 11% were expected to be Hispanic or Latino. For the second half of the project, per supplementary funding to improve study diversity to better reflect the greater Los Angeles population (see Section 11), we aim to recruit a second-half cohort to be 35% non-Hispanic white, 17% non-Hispanic black, and 40% Hispanic. We expect to randomize 10 participants per month over 36 months.

Prospective participants will be referred by physicians at the designated clinical sites or identified using the Deep 6 AI® cohort building software, which uses natural language processing to search the Cedars-Sinai EHR for patients who meet the study's inclusion and exclusion criteria. We anticipate screening 800 potential participants in order to randomize 360. Recruitment of women is not expected to be a problem, because patients seeking care for cLBP are disproportionately female. Women who are pregnant or planning to become pregnant are not excluded from participating. Race and ethnicity of enrolled participants will be tracked monthly. If the proportion of minority participants appears to be lagging, the number contacted will be increased.

Eligible potential participants will be sent an IRB- approved recruitment letter explaining the study via email. For individuals identified via cohort builders who have seen a physician partnered with the study staff, a personalized letter bearing their treating physician's voice and signature will be used; all other cohort builder identified individuals will be sent a letter from the primary investigator. An informational study brochure will also be attached. The recipient may opt-out of further contact by replying to the email.

Research coordinators will monitor participant compliance with the survey questionnaires using an automated dashboard. Participants will be encouraged to remain in the study and complete the questionnaires using a combination of email reminders, telephone calls, and/or SMS text messages. from research coordinators. *Study coordinators will contact the participant following non-completion of a survey if >1 week has elapsed since the initial survey send date.* Technical support will be available throughout the study.

Participants will be eligible for up to \$225 in Amazon gift card codes throughout the study after randomization. After completing 80% of the first month of surveys, participants will be sent a \$25 Amazon gift card code. After completing 75% of the second month of surveys, participants will be sent another \$25 Amazon gift card code. Once the participant completes 80% of the surveys in the 3rd month and returns the equipment, they will be sent a \$175 Amazon gift card code along with recommendation for VR equipment that could be purchased after the end of the study. The \$175 Amazon code compensation will not be released until the audiovisual headset and Fitbit device has been returned.

Participants will be emailed recommendations for hardware and software that can be used after the study once the equipment has been returned in the email with the Amazon codes.

A detailed description of the recruitment and retention process is in section 5.1 and 5.2 of the MOOP.

## 6 STUDY INTERVENTION

### 6.1 STUDY INTERVENTION(S) ADMINISTRATION

### 6.1.1 STUDY INTERVENTION DESCRIPTION

The two active interventions evaluated in this study are 360-degree, 3-D therapeutic visualization programs (EaseVRx and EaseVRx-Distraction) delivered via a commercially available VR headset. The control intervention consists of 2-D visualizations delivered by the same VR headset. The three software programs were developed by AppliedVR. The EaseVRx programs are not currently regulated by the FDA. In September 2019, AppliedVR was awarded two grants by NIDA to conduct proof-of-concept studies to evaluate EaseVRx and EaseVRx-Distraction as opioid-sparing tools for acute and chronic pain. The results of these studies will inform the company's regulatory pathway with the FDA. Following are descriptions of the three programs:

#### Skills-Based VR: EaseVRx

EaseVRx was developed by AppliedVR in partnership with pain psychologist [name], Associate Professor of Anesthesiology, Perioperative and Pain Medicine at Stanford University and an NIH- and PCORI-funded investigator in the use of VR for pain management. EaseVRx incorporates the evidence-based principles of CBT, mindful meditation, and physiologic biofeedback therapy using embedded biometric sensors. It combines psychoeducation, pain education, breathing training, relaxation exercises, and executive functioning games to provide a mind-body approach toward living better with chronic pain. The standardized, prescriptive, and reproducible 56-day program delivers a combination of skills training and CBT-related treatments through scheduled daily virtual experiences. The participants are allowed to complete as many sessions as they would like. In addition to the prescribed schedule of content the participant will have access to the full library of content. Each VR experience lasts between 2-16 minutes, with an average duration of 6 minutes. The VR treatment modules are designed to minimize triggers of emotional distress or cybersickness. There are 5 types of modules:

- **Interoceptive:** These modules are designed to help the user understand and perceive what is happening inside the body. They provide a biofeedback-like platform in which the changes in the observed environment reflect a progressively enhanced state of relaxation.
- **Education:** Help the user understand why the VR exercises are relevant to their pain, as well as teaching specific topics often used in pain psychology, including the neurobiology of pain, the role of mood and stress in pain, pain catastrophizing, activity pacing and setting goals. The goal is for the user to create self-management steps and a toolkit of strategies they can use to manage their response to pain.
- **360-degree videos:** High-quality 360 videos with voiceovers, music, and sound effects that are designed to maximize relaxation and engagement of users.
- **Game modules:** Games are designed to maximize distraction and engagement, increasing the cognitive load on patients, and decreasing their perception of pain.
- **Dynamic breathing:** These modules are based on evidence-based biofeedback training designed to enhance awareness of one's physiological response to pain and to self-regulate that response. In a virtual world, the user experiences a gamified biofeedback session in which they are introduced to awareness of their breath via visualization in the form of air bubbles. In multiple sessions, the user receives increasingly challenging tasks to practice diaphragmatic breathing while interacting with the virtual environment. The user is also asked to pace their breath according to an expanding and contracting ring in the environment to slow the breath and create physiological changes associated with relaxation. The user's exhale is measured by the microphone embedded in the headset, offering biodata-enabled immersive therapeutics.

#### Distraction-Based VR: EaseVRx-Distraction

EaseVRx-Distraction has the same number of experiences, the same approximate duration of experiences, and the identical user interface as EaseVRx, with a linear prescribed sequence of experiences. The key difference is that instead of offering a variety of VR experiences including education, games, and breath biofeedback, EaseVRx Distraction only includes 360-degree videos - which are also present in EaseVRx. This is intended to remove the effect of education and skills-based training, while preserving the immersive experience of 360-degree VR.

#### **Sham VR: EaseVRx-Sham**

EaseVRx Sham software includes 2D nature footage accompanied by neutral music that is selected to be neither relaxing nor distracting, rather than 360-degree, 3D, interactive content specially selected for efficacy. The experience of using EaseVRx-Sham is similar to watching a large-screen TV, but it is not interactive or immersive. EaseVRx Sham has the same number and duration of experiences as EaseVRx, and the functionality of the user interface used to access the experiences is the same. Modifications were made to the appearance of the user interface in order to remove aspects that were added for therapeutic benefit.

The study intervention will be delivered using a commercially available VR headset, the PICO G2 4K ([https://www.pico-interactive.com/us/G2\\_4K.html](https://www.pico-interactive.com/us/G2_4K.html)). The headset battery requires recharging after approximately 2.5 hours of use.

AppliedVR has created videos to help participants understand how to use the headset and cover trouble-shooting issues with the headset and software. The Cedars-Sinai study team also will provide technical support.

---

#### **6.1.2 DOSING AND ADMINISTRATION**

All participants are instructed to use the VR program at least once a day and as needed throughout the first eight weeks. Thereafter, the participant can use the program as needed. Section 4.3 provides the justification of dose.

---

### **6.2 PREPARATION/HANDLING/STORAGE/ACCOUNTABILITY**

---

#### **6.2.1 ACQUISITION AND ACCOUNTABILITY**

The PICO VR headsets loaded with the EaseVRx software programs will be provided by AppliedVR. The devices will be managed by the research team at Cedars-Sinai Medical Center.

---

#### **6.2.2 FORMULATION, APPEARANCE, PACKAGING, AND LABELING**

N/A

---

#### **6.2.3 PRODUCT STORAGE AND STABILITY**

The PICO VR headsets will remain in the boxes supplied by AppliedVR until they are shipped to participants.

---

#### **6.2.4 PREPARATION**

Prior to shipping the VR headset to a study participant, the headset battery will be checked to make sure it is fully charged. Any headsets that are handled by staff will be sanitized by cleaning the fabric surfaces using Virex, the plastic housing using Sani-Wipes, and the glass lenses using alcohol-based lens cleaner.

### 6.3 MEASURES TO MINIMIZE BIAS: RANDOMIZATION AND BLINDING

We will allocate study participants using a random number generator to assign blocks of 3, 6, 9, or 12 to ensure there is an equal distribution in the EaseVRx skills-based group vs. the EaseVRx-Distraction group vs. the EaseVRx-Sham group. Participants, their clinical providers, and study statisticians will be blinded to the study arm. The groups will be labeled as A, B or C at random. A clinical research coordinator will ship the headset containing the assigned program to the participant and enter the group label into the log of enrolled participants. Datasets will be provided to the statistician using these group labels. The research coordinator who maintains the list of randomization assignments will not call participants on the telephone. Because the intervention is conducted in participants' homes and the data are collected remotely, the participants will not encounter each other and thus will be less likely to guess their study arm assignment. We anticipate there will be no circumstances during the study that require unblinding of an individual participant or a whole group because we do not expect any related SAEs to occur with this low risk intervention.

We have restructured the block randomization module within REDCap with stratification based on the 4 sites of recruitment (1 – pain clinic, 2 spine clinic, 3 – rheumatology clinic, 4 – Deep6). Randomization will be performed on a 1:1:1 basis across the 3 treatment groups and stratified across the 4 treatment sites with random block sizes (3, 6, 9, or 12). Allocation tables will be generated using STATA v16 software and uploaded into REDcap for patient allocation.

### 6.4 STUDY INTERVENTION COMPLIANCE

Data collection will be monitored daily by the study team. Participants initially will be sent a reminder email when they have completed no survey questionnaires 2 days after the survey is distributed. If the participant does not respond to the email two additional 48-hr reminders will be sent. A team member will call the participant on the next business day. If no data are received. They will be asked why they have missed all three reminders and encouraged to continue to complete surveys as they are sent. If the participant does not complete any surveys in the next 72hrs they will be sent a final email with a link to the last survey. The participant will not be contacted again until the end of study to request a return of equipment.

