### 7.3 LOST TO FOLLOW-UP

A participant will be considered lost to follow-up if he or she fails to schedule an onboarding phone call within 30 days of device delivery or if he or she fails to complete the initial SSQ+ survey within 30 days of onboarding completion. For participants who complete the initial SSQ+ survey, fail to complete >80% of future surveys, and become unreachable by phone or email, the participant will be considered lost to follow-up 6 days following the email date of the participant's Day 90 survey.

If a participant fails to complete the Day 90 survey within six days, the following actions will be taken:

- The research coordinator will attempt to contact the participant and counsel them on the importance of completing surveys and returning the equipment to be eligible for the gift card.
- Before a participant is deemed lost to follow-up, the investigator or designee will make every effort to regain contact with the participant (where possible, 3 telephone calls and, if necessary, a certified letter to the participant's last known mailing address or local equivalent methods). Contact attempts will be documented in the participant's study record.
- Should the participant continue to be unreachable, he or she will be considered to have withdrawn from the study with a primary reason of lost to follow-up.

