### 8.3.3 CLASSIFICATION OF AN ADVERSE EVENT

#### 8.3.3.1 SEVERITY OF EVENT

For adverse events (AEs) the following guidelines will be used to describe severity.

- **Mild** – Events require minimal or no treatment and do not interfere with the participant's daily activities.
- **Moderate** – Events result in a low level of inconvenience or concern with the therapeutic measures. Moderate events may cause some interference with functioning.
- **Severe** – Events interrupt a participant's usual daily activity and may require systemic drug therapy or other treatment. Severe events are usually potentially life-threatening or incapacitating. Of note, the term "severe" does not necessarily equate to "serious".

Research staff will call the patient if an event is noted in an event assessment that is sent on a weekly basis. Nothing more than mild side effects that do not require medical treatment are expected.

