- Inconsistent, improperly formatted, or out-of-range dates; and
- Fields on a "completed form" not completed.

Once the study begins, routine QC reports will be prepared monthly (with 2 weeks lead-time before proposed monthly uploads to DAC) by the study statisticians. These reports will describe target and actual enrollment, eligibles screened with reasons for screen failure, and participant disposition (enrolled; active, completed, discontinued treatment, and lost to followup). These reports will also provide proportions of forms completed/missing, as well as summaries of problems identified by QC processes. Changes to QC programming will be documented and re-tested for accuracy.

Finally, daily monitoring for data completeness will be undertaken by the study team as a QA effort. Patients will initially be sent a reminder email when they have not submitted data after 2 days. If no response is given two additional 48-hr reminders will be sent. Research staff will attempt to contact the patient up to 3 times in one week.

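### Protocol 6.4 ends contact with a non-responder until the end of study, with no exception for the Day 30, 60 or 90 surveys, and so contradicts 5.5

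*Protocol*

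**What the plan says.** **Protocol 6.4.** A participant who has completed nothing 2 days after a survey goes out gets a reminder email, then two more at 48-hour intervals. A call follows on the next business day, in which the participant is "encouraged to continue to complete surveys as they are sent". After that: "If the participant does not complete any surveys in the next 72hrs they will be sent a final email", and then "The participant will not be contacted again until the end of study to request a return of equipment".

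**Protocol 5.5.** "Study coordinators will contact the participant following non-completion of a survey if >1 week has elapsed" since it was sent. There is no limit on how often this applies and no point at which it ends.

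**Protocol 8.1.** Participants who leave surveys incomplete get a reminder prompt. No cut-off is given.

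**Protocol 10.1.8.** It restates the same email sequence but ends differently: "Research staff will attempt to contact the patient up to 3 times in one week".

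**Protocol 7.3.** After a missed Day 90 survey, "The research coordinator will attempt to contact the participant and counsel them on the importance of completing surveys and returning the equipment". It also classes a participant as lost to follow-up early if he or she "fails to schedule an onboarding phone call within 30 days of device delivery", or does not complete the first SSQ+ survey within 30 days of onboarding.

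**Schedule of Activities (1.3).** Pain interference is surveyed on Days 1, 7, 15, 21, 30, 45, 60, 75 and 90, each with a +6-day window.

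**The concern.** Day 30 pain interference is the primary endpoint. Day 90 is the time point for inference on all four patient-reported secondary endpoints (pain interference, sleep disturbance, anxiety, PCS SF-6). The analysis population is all randomised patients. A rule that stops pursuing people who fall silent early, and exempts no survey, withdraws effort where the analysis most needs data. It also sits badly with 7.2, which invites people who stop using the headset to keep answering surveys.

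What is at stake is avoidable missing data at Days 30, 60 and 90. That missingness could be related to early experience with the headset, though the documents hold no evidence on this. There is also a conduct problem: two coordinators, one following 5.5 and one following 6.4, would treat the same participant differently, and the report could not say which rule produced the data.

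**Working it through.** The plan gives no figure for Day 30 non-response or for how many reach the stop, so there is none to reproduce. The check is date arithmetic on nominal survey days.

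**Inputs (Protocol 6.4 and 1.3).** For a survey sent on day *s*:
- reminders at *s*+2, *s*+4 and *s*+6;
- call on the next business day after *s*+6: *s*+7, or up to *s*+9 if *s*+6 is a Friday;
- final email and stop 72 hours after the call: *s*+10 to *s*+12.

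| Unanswered survey | Call | Stop | Next scheduled survey at the stop |
|---|---|---|---|
| Day 1 | 8-10 | 11-13 | Day 7, already out 4-6 days |
| Day 7 | 14-16 | 17-19 | Day 15, already out 2-4 days |
| Day 15 | 22-24 | 25-27 | Day 21, already out 4-6 days |
| Day 21 | 28-30 | 31-33 | Day 30, already out 1-3 days |
| Day 30 | 37-39 | 40-42 | Day 45, due in 3-5 days |
| Day 45 | 52-54 | 55-57 | Day 60, due in 3-5 days |
| Day 60 | 67-69 | 70-72 | Day 75, due in 3-5 days |
| Day 75 | 82-84 | 85-87 | Day 90, due in 3-5 days |

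**If 6.4 governs, what is lost.**
- Day 30 reminders fall on Days 32, 34 and 36. Stops on Days 11-13, 17-19 and 25-27 precede all three. A stop on Day 31-33 removes two or three of them.
- Day 90 reminders fall on Days 92, 94 and 96. Every stop in the table precedes them.
- Day 60 reminders fall on Days 62, 64 and 66. Of the four later stops, those following the Day 30 and Day 45 surveys precede them.

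**How many misses it takes.** The stop requires that no survey be completed in the 72 hours after the call. Before Day 30 the next survey is already out by then, so it too must be unanswered. From Day 30 the surveys are 15 days apart and the sequence takes 10-12 days, so one unanswered scheduled survey suffices. This assumes that the weekly event assessments (8.3.3.1) do not count as surveys. If they do, they must also go unanswered.

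**6.4 against 5.5.** For the first missed survey the two roughly agree: a call at +7 to +9 days against contact after more than 7 days. For any survey missed after the stop, 5.5 requires contact and 6.4 forbids it.

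**Is there still time to act?** Section 8.1 plans the last randomisation for 9/5/2023. If days run from randomisation, the last Day 30, 60 and 90 windows close at +36, +66 and +96 days: 10/11, 11/10 and 12/10/2023. If Day 1 is an onboarding call 30 days later (10/5/2023, shipping ignored), Days 36, 66 and 96 fall on 11/9/2023, 12/9/2023 and 1/8/2024. This protocol version is dated 19 October 2023. On the first clock Day 30 has passed for everyone; on either clock Day 60 and Day 90 windows are still open.

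**The case against.** The strongest reply is that 6.4 is one of several texts and nothing says it overrides the others. Sections 5.5 and 8.1 both promise contact or a prompt without a cut-off, and 5.5 refers detailed procedure to the MOOP, which is not available here. The summary of changes lists 5.5, but not 6.4, for the revision of compliance procedures, so 6.4 may be leftover wording. Nor can its last sentence be fully literal: "Research staff will call the patient if an event is noted in an event assessment that is sent on a weekly basis", and a depression alert triggers a physician's call (8.2). Limiting contact with persistent non-responders is also a legitimate way to limit burden. All of this stands. It makes the loss of reminders conditional on 6.4 being the rule followed; it does not remove the contradiction.

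Four stronger readings are tempting, and the documents do not support them:

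- **Surveys stop being sent.** 6.4 speaks of surveys continuing as scheduled and does not say they cease.
- **One missed survey before Day 30 ends follow-up.** The overlap in the table shows that at least two must go unanswered.
- **The call comes too late because it falls after the +6-day window.** No text says a later survey is refused. The final email at +10 to +12 days carries a link to the last survey, which suggests late completion is accepted.
- **Power is lost.** Section 9.2 has no dropout allowance, but no Day 30 missing rate is given, so no loss can be computed.

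The early lost-to-follow-up rule also narrows the Day 1 case. With onboarding on Day 1, a participant who never completes the SSQ+ survey is lost to follow-up at about Day 31 (1 + 30), before the first Day 30 reminder on Day 32.

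**Conclusion.** The contradiction between 6.4 and 5.5 is real for every survey missed after the stop, and 7.3, 8.1 and 10.1.8 also need reconciling with 6.4. The consequence is conditional. If 6.4 is followed, early non-responders get no staff reminder for the primary endpoint survey, and from Day 30 on a single unanswered scheduled survey removes the reminders for Day 90.

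This rests on nominal survey dates and on event assessments not counting as surveys. The number of participants affected is unknown, and any link between the missingness and treatment experience is a possibility only. The change is worth making because it is cheap and because, on the planned dates, Day 60 and Day 90 surveys were still due after this version's date. Confidence is medium, since the MOOP may already settle the matter.

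**What to change.** Replace the last sentence of 6.4 with:

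*Participants who have not withdrawn, opted out of contact or been classed as lost to follow-up under 7.3 continue to be sent all scheduled surveys, and the reminder sequence restarts for the Day 30, 60 and 90 surveys whatever was missed earlier.*

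Then:
- Bring 5.5, 7.3, 8.1 and 10.1.8 into line with it: the number of attempts, the cut-off if any, and whether end-of-study contact covers surveys as well as equipment.
- If the call is meant to fall inside the +6-day window, change the reminder timing in 6.4 too. With the third reminder at +6 and the call on the next business day, it cannot.
- Where Day 30 has already passed, apply the rule to the remaining Day 60 and Day 90 surveys.
- State in SAP 5.1, now a placeholder, which contact rule was used. Report by arm in the SAP 4.2 disposition summary how many had follow-up stopped before Day 36.

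Cost: one replaced sentence, matching edits in four sections, one line and one table row in the SAP, a few extra emails and calls by existing coordinators, and slightly more participant burden.
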